## 11.0 SAFETY ANALYSES

The safety endpoints of this study are defined in **Section 4.5**.

### 11.1 Adverse Events

Analyses of adverse events (AEs) will include all adverse events in the present study, not just treatment emergent AEs (e.g., if a placebo patient has an AE starting in C-935788-047/C-935788-048 studies and continuing in the present study, this AE will be included in the analyses) . Adverse events will be coded using the Medical Dictionary for Regulatory Activities (MedDRA 19.1). The number of events and the number and percentage of patients with at least 1 adverse event, at least one severe AE, at least one moderate or severe AE, at least 1 serious adverse event (SAE), at least 1 treatment related adverse event, at least one adverse event leading to dose reduction, at least one adverse event leading to dose interruption, at least one adverse event leading to drug withdrawal, and at least one adverse event leading to death will be presented. AEs that are possibly or probably related to study treatment, or for which the relationship to study treatment is missing, will be considered treatment related. Among patients with at least one AE, the mean number of AEs per patient will also be presented. The number and percentage of patients with adverse events of interest [any gastrointestinal (GI) complaints (nausea, vomiting, diarrhea, abdominal pain), overall and separately, infection, hypertension, neutropenia, transaminase elevation, and bilirubin elevation] will be presented. For the AEs of nausea, vomiting, abdominal pain, and infection, Rigel will specify preferred terms that fit into these categories. AEs, SAEs, AEs of interest, AEs leading to dose reduction, AEs leading to dose interruption, AEs leading to drug withdrawal, and AEs leading to death will be summarized at the patient level by MedDRA system organ class (SOC) and preferred term using frequencies and percentages. AEs will also be tabulated at the event level and the patient level by severity

and by causal relationship to study drug. AEs of interest will be tabulated at the event level and the patient level by severity.

Regarding diarrhea (as reported by SMQ 19.1), the following additional analyses will be performed:

- A patient's maximum diarrhea severity grade for the post-baseline period will be summarized using counts and percentages.
- A patient level of listing for diarrhea that include the diarrhea severity grade, diarrhea start and end dates and duration of diarrhea in the present study will be provided.

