4.4 Safety Endpoints

Safety endpoints include the frequency and severity of bleeding according to the IBL5; change from baseline (baseline value is the value at the initiation of active therapy) in blood pressure, liver function, and ANC; the incidence and severity of gastrointestinal (GI) effects (nausea, vomiting, diarrhea, abdominal pain); infection; and overall AEs.

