6.0 SUBJECT SELECTION

6.1 Inclusion Criteria

1. Subject must be willing and able to give written informed consent by signing an IRB-approved Informed Consent Form prior to participating in any study-specific procedures.
2. Subjects must have completed the Week 24 evaluation of Study C-935788-047 or C-935788-048 or have discontinued early (starting at Week 12) due to lack of response. No more than 7 days may have elapsed between the last day of treatment on the Study C-935788-047 or C-935788-048 and initial dosing (Day 1) in Study C-935788-049.
3. Male or female at least 18 years of age.
4. Females must be either postmenopausal for at least 1 year or surgically sterile; or if female of child-bearing potential, must not be pregnant or lactating and must agree to use an acceptable method of birth control throughout the duration of the trial and for 30 days following the last dose. Acceptable methods of birth control are defined as: hormonal contraception (pill, injection or implant) used consistently for at least 30 days prior to enrollment, intrauterine device (IUD), double-barrier (ie, condom and spermicide, or condom and diaphragm), or complete abstinence.
5. In the Investigator's opinion, the subject has the ability to understand the nature of the study and any hazards of participation and to communicate satisfactorily with the Investigator.

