9.2.1 Adverse Event Reporting Period

The AE reporting period begins from the last dose of study drug in Study C-935788-047 or C-935788-048 and ends with the final study (Follow-Up) visit in the Study C-935788-049. All ongoing AEs from Study C-935788-047 or C-935788-048 will be followed as AEs in Study C-935788-049.

If an SAE is present at the Follow-Up Visit, it should be followed to resolution or stabilization unless the subject is lost to follow-up. Resolution means the subject has returned to baseline state of health or the Investigator does not expect any further improvement or worsening of the event.

In case of ongoing SAEs at the moment of database closure, the data obtained at the moment of database closure will be used in the statistical analysis. The follow-up of the SAE will be documented in the source documents and will be described in the final report or as an addendum as appropriate.

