### **5.8. Definition of Baseline Measurements**

For the summary of baseline characteristics of present study, the baseline characteristics used for summary are defined in **Section 4.1** and **4.2**.

For the calculation of change from baseline, the baseline value is defined as the last measurement for the corresponding variable prior to the first dose of fostamatinib in Study C-935788-047 or C-935788-048 (for fostamatinib patients in the previous study) or the present study (for placebo patients in the previous study).

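### The adverse event tables count placebo-onset events with fostamatinib-onset events and use neither a prior-treatment split nor person-time, and the mean bleeding score stops at 24 months in a study scheduled to Month 60

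*SAP*

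**What the plan says.** **Adverse events.** SAP 11.1 sets the scope: "Analyses of adverse events (AEs) will include all adverse events in the present study, not just treatment emergent AEs". Its own example is "if a placebo patient has an AE starting in C-935788-047/C-935788-048 studies and continuing in the present study, this AE will be included". The treatment-related row takes "AEs that are possibly or probably related to study treatment" and also events whose relationship is missing. Results are numbers of events and counts and percentages of patients. The section requests no onset-based subset, no split by prior treatment and no patient-years.

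Protocol 9.2.1 supports the carry-over: "All ongoing AEs from Study C-935788-047 or C-935788-048 will be followed as AEs in Study C-935788-049". It also says "The AE reporting period begins from the last dose of study drug in Study C-935788-047 or C-935788-048". Inclusion criterion 2 (protocol 6.1) allows a gap before the first 049 dose: "No more than 7 days may have elapsed between the last day of treatment". Protocol 9.1, however, confines AEs in this study to treatment-emergent events, either new or a detectable worsening. SAP 3.5, which lists departures from the protocol's analyses, does not mention AE scope.

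**Prior treatment and exposure.** SAP 5.1 defines the prior study treatment group and restricts analyses to 049 data, with a few exceptions; AEs are not among the examples it names. SAP 10.3, 11.4 and 12.5 ask for results by prior treatment group. SAP 9.0 summarizes duration of dosing but does not connect it to AEs.

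**Bleeding score.** SAP 11.4 averages the IBLS over a treatment period of 24 months. Protocol 10.5 averages it over the treatment period with no such limit, and the visit schedule in both documents runs to Month 60.

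**The concern.** Long-term safety is the primary objective, so the AE tables are a core output. For a prior-placebo patient, fostamatinib begins at the first 049 dose. An event that began earlier cannot have been caused by the drug, yet it adds to the AE percentage and possibly to the treatment-related percentage. With no fostamatinib-onset table alongside, a reader of the report cannot separate the two kinds of event.

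An overall percentage also combines patients at different stages. Prior-placebo patients are starting the drug. Prior-fostamatinib patients have already taken it, and any of their AEs that resolved in the parent study are not counted. If a risk is concentrated at drug start, the pooled figure understates it for new starters. Protocol 3.6.1 reports that blood pressure rises in the rheumatoid arthritis trials generally came early, so this is a plausible pattern for at least one AE of interest. Without person-time, the percentage cannot be read as a risk over a stated time on drug.

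The IBLS limit works differently: it removes late data from exactly the patients who show what long treatment looks like.

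**Working it through.** The plan gives no figure to reproduce on this point. The AE parts rest on setting the sections side by side; the IBLS part is a visit count.

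**1. Which events enter the AE tables for a prior-placebo patient**

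- Onset on placebo, ongoing at 049 entry: counted (SAP 11.1; protocol 9.2.1).
- Onset after the last placebo dose and before the first 049 dose, a gap of up to 7 days (protocol 9.2.1 with inclusion criterion 2): falls in the 049 AE period, so counted, although no fostamatinib has been taken.
- Onset on or after the first 049 dose: counted.

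Only the third class began on the drug. SAP 11.1 plans no table restricted to it.

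**2. Size of the carry-over**

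The share of treated patients who bring in a placebo-onset AE is (share of prior-placebo patients) × (fraction of them with an ongoing AE). The documents give neither input. Purely as assumptions, take 25–50% for the first and 5–20% for the second:

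- low: 0.25 × 0.05 = 1.25%, about 2 of 150 patients
- high: 0.50 × 0.20 = 10%, or 15 of 150 patients

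This is not an estimate for 049. Some of these patients would have another AE anyway, so the effect on the row for any AE could be smaller.

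**3. Why person-time matters**

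At a constant event rate h, the expected proportion with an event by time t is 1 − exp(−h·t). It rises with t even when h does not change. Treatment can last up to 60 months (protocol 7.1.2), and a patient may stop at any time by own decision or for an AE (protocol 7.9). The crude percentage therefore depends on the mix of follow-up times as well as on risk. The documents do not give that mix.

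**4. IBLS assessments lost to a 24-month limit**

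Inputs from the schedule of procedures: monthly visits for Months 1–18, then every other month to Month 60, taken as Months 20, 22, …, 60. Day 1 and the Follow-up visit are not counted.

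- Total: 18 + 21 = 39
- By Month 24: 18 + 3 = 21
- After Month 24: 39 − 21 = 18

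| Treated to month | Scheduled assessments | After Month 24 | Share lost |
|---|---|---|---|
| 30 | 24 | 3 | 12.5% |
| 36 | 27 | 6 | 22% |
| 48 | 33 | 12 | 36% |
| 60 | 39 | 18 | 46% |

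The last row is a ceiling, because treatment ends sooner if the drug becomes commercially available.

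**The case against.** The strongest defence is that the AE rule is open and deliberate. It carries out protocol 9.2.1, and counting events that predate the drug overstates its AEs, which is the cautious direction. That stands as a reason to keep the all-AE tables. It does not replace a fostamatinib-onset table, and the caution does not extend to pooling, which can hide risk at drug start. It could be added that protocol 9.1 does not say which treatment an event must emerge on. But SAP 11.1 itself presents its rule as going beyond treatment-emergent events, and SAP 3.5 is silent.

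The missing split is an inference from silence in SAP 11.1. There are no table shells, and SAP 5.1 sorts listings by prior treatment group, so the data will be visible patient by patient. The inference is still reasonable, because other sections request the split by name. No document promises patient-year rates; asking for them is a recommendation and not the correction of a contradiction. By-visit laboratory and blood pressure summaries already show time course.

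Three stronger readings are tempting but not supported:

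- A reader might infer that SAP 11.1 contradicts SAP 5.8 ("the baseline value is defined as the last measurement for the corresponding variable prior to the first dose of fostamatinib") and protocol 4.4 ("baseline value is the value at the initiation of active therapy"). Both define a baseline for change scores; neither sets a rule for AE onset.
- A reader might take exposure to run from 12 weeks to 60 months and quote the ratio. The 12 weeks in protocol 7.3 concern nonresponders, and protocol 7.9 allows earlier withdrawal, so there is no such lower bound.
- A reader might use protocol Table 1 to show how far percentages and patient-year rates differ for this drug. For one arm the ratio is 723/288 = 2.5, which only reflects mean follow-up in a rheumatoid arthritis population. It says nothing about 049, and no comparison with that table is planned.

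On the IBLS, the 24 months look like carried-over wording, and the highest and total scores by visit have no such limit. That narrows the effect to one descriptive mean, but as written the limit would still be programmed.

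**Conclusion.** The point holds in three limited parts.

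- The AE and treatment-related percentages can include events that began before any fostamatinib, with no onset-based table beside them. This sits badly with protocol 9.1 and is not declared in SAP 3.5.
- SAP 11.1 requests neither a prior-treatment split nor person-time, so a crude overall percentage mixes new starters with patients already exposed. This part rests on the silence of SAP 11.1 read against the other sections.
- The mean IBLS, read literally, omits from 12.5% (30 months) to at most 46% (60 months) of a long-treated patient's scheduled assessments. The by-visit IBLS summaries are unaffected.

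The size of the first two effects cannot be computed from the documents. They may act in opposite directions, so the net direction is also unknown. Nothing here shows that the reported percentages will be badly wrong; they will be hard to interpret for the study's primary objective.

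**What to change.** **SAP 11.1**

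- Base the main AE tables on events with onset or worsening on or after the first fostamatinib dose, by prior study treatment group and overall.
- Add a footnote that the prior-fostamatinib column includes ongoing 047/048-onset events but not events resolved before 049, so the two columns are not directly comparable.
- List separately the continuing placebo-onset events and, for prior-placebo patients, events in the gap before the first 049 dose.
- Keep the all-AE tables as supportive, for continuity with the interim analysis made for the New Drug Application. Record the change in SAP 3.5.
- For SAEs and AEs of interest, add patients with a first 049-onset event per 100 patient-years, by prior treatment group. Count person-time from the first 049 dose to the first such event, the Follow-up visit or database lock, whichever comes first. Remove patients with that AE ongoing at 049 entry from both numerator and person-time. State that time in 049 equals time since first fostamatinib only for the prior-placebo group. A few broad time intervals are optional.

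**SAP 11.4**

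- Define the mean IBLS over the full treatment period, as in protocol 10.5. The WHO scale may keep 24 months, because protocol 7.6.4 says that it was collected in the first 2 years and then discontinued.
- The 24-month statements (SAP 3.2, protocol 8.4) and the 60-month statements (protocol 5.3, 7.1.2) must be reconciled.

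**Cost.** SAP wording, one listing, extra table columns and one rate table, all from data already collected. AE counts may differ from the interim displays, and late rates will be imprecise with at most 150 patients.

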## 11.2 Clinical Laboratory Tests

Descriptive statistics will be presented by scheduled visit for the actual values and the changes and percentage changes from baseline for each selected quantitative laboratory test (hematology, serum chemistry, and liver function test). Actual values of categorical urinalysis test results will be summarized by scheduled visit. Lab values that are out of normal range will be flagged in the data listings.

Box plots indicating mean and median as well as the 25th and 75th percentiles, reference plots, and spaghetti plots will be presented by study scheduled visit for both raw values and changes from baseline.

Descriptive statistics for the actual values, changes from baseline, and maximum value observed post baseline will be presented by scheduled visit in the present study. In addition, two types of shift tables based on lab values classified per Common Terminology Criteria for Adverse Events (CTCAE) Grade Version 5.0 will be provided as follows:

- Grades based on baseline lab values vs. the grades based on the worst post-baseline lab values observed in the present study,
- Grades based on baseline lab values vs. the grades based on the last post-baseline lab value observed in the present study.

These two types of shift table summaries above will be applied to the following selected lab parameters, respectively:

- Liver function tests (i.e., ALT, AST, total bilirubin and indirect bilirubin)
- Absolute neutrophil count (ANC)
- Alkaline Phosphatase

Regarding lab values of ALT, the following additional analyses will be performed:

- Descriptive statistics for the average number of events of lab value increasing from baseline for each patient.

- Frequencies and percentages for number of patients with the events of lab value increasing from baseline

Same additional analyses will be performed for AST.

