Appendix 2: Management of Neutropenia

Based on data from previous clinical studies, treatment with fostamatinib may be associated with lowering of ANC.

A decrease in ANC may require adjustment of the dose of study drug. Follow the dose adjustment guidelines as outlined below when adjusting the dose of study medication.

Dose Adjustment

Dose	Dose Level -1	Dose Level -2	Dose Level -3 ^a	Dose Level -4 ^a
100 mg PO bid	150 mg PO qd	100 mg PO qd	discontinue	----
150 mg PO bid	100 mg PO bid	150 mg PO qd	100 mg PO qd	discontinue

^a The Sponsor's Medical Monitor should be consulted prior to consideration of dose modification to levels -3 or -4.

Decrease in ANC to < 1,000/ μ L:

- Repeat ANC within 72 hours.
- If repeat testing confirms that ANC is < 1,000/ μ L, immediately interrupt study drug administration.
 - Repeat ANC at 72 hour intervals.
- When ANC recovers to > 1,500/ μ L, restart study drug at dose level -1.

Second event of ANC < 1,000/ μ L:

- Confirm ANC as above.
- If confirmed, immediately interrupt study drug until ANC > 1,500/ μ L.
- Restart study drug at dose level -2.

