## **5.0 STATISTICAL METHODS**

### **5.1 General Considerations**

The statistical analysis for this study will be performed using SAS® version 9.4 or higher. All one-sided statistical tests will be performed at the 0.025 significance level, and all two-sided tests will be performed at the 0.05 significance level, unless otherwise indicated.

Prior study treatment group will refer to the patient's randomized treatment group (fostamatinib or placebo) from the previous study in which the patient participated. Unless otherwise specified.

Analyses will be based on only the data from the present study (C935788-049), except for the baseline value and a few other exceptions (e.g., duration of platelet response, primary efficacy endpoint, and the platelet count by-visit summary).

Data collected in this study will be documented using summary tables and patient data listings. Continuous variables will be summarized using descriptive statistics, specifically the mean, median, 25th percentile (Q1), 75th percentile (Q3), standard deviation, minimum and maximum. Categorical variables will be summarized using frequencies and percentages.

Data listings will be sorted by prior study treatment group and patient ID number. All date fields will be presented in a format of ddmmyyyy (i.e., 01Jan2014) in the listings. All data will be included in the data listings.

As a global note, platelet counts taken within 28 days of rescue therapy will be excluded from any platelet count related analyses.

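### SAP 11.2 takes the maximum as the post-baseline extreme for every laboratory test, which is the least adverse value for blood counts, and leaves WBC, lymphocytes and hemoglobin without any per-patient worst-value summary

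*SAP*

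**What the plan says.** SAP 11.2 opens with by-visit summaries of actual values, changes and percentage changes for selected hematology, chemistry and liver tests. A later sentence lists descriptive statistics for actual values and changes from baseline, and adds that the "maximum value observed post baseline will be presented by scheduled visit in the present study". Nothing limits this sentence to tests where a rise is the harm, and the SAP names no per-patient minimum for any laboratory test.

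The same section plans two CTCAE version 5.0 shift tables. The first is "Grades based on baseline lab values vs. the grades based on the worst post-baseline lab values observed in the present study"; the second uses the last post-baseline value. Their scope is restricted: "These two types of shift table summaries above will be applied to the following selected lab parameters, respectively". The list holds ALT, AST, total bilirubin, indirect bilirubin, ANC and alkaline phosphatase.

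On direction, Protocol Appendix 2 states that "treatment with fostamatinib may be associated with lowering of ANC", and Protocol 4.4 makes change from baseline "in blood pressure, liver function, and ANC" a safety endpoint. SAP 4.5 lists abnormal laboratory changes by CTCAE criteria as a safety endpoint and gives hematology and chemistry as its examples.

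**The concern.** Long-term safety is the study's primary objective, and for laboratory data the extreme value reached by each patient is a standard way to show it. An extreme is informative only if it is taken in the direction of harm. For ANC the single numeric extreme that the SAP names points the other way: a patient whose count drops and recovers looks the same in that column as a patient whose count never moved. A reader of the report could take the column as reassurance.

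The wording also leaves the programmer to guess, because a maximum over the whole post-baseline period does not belong to any one visit. For counts outside the shift-table list, no other planned table gives a per-patient worst value.

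**Working it through.** The SAP gives no figure to reproduce here, so the check sets its sections side by side.

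1. **How many values feed the maximum.** The schedule (SAP Table 1, Protocol Table 2) has no hematology at Month 1, monthly draws in Months 2–18 and draws every other month in Months 19–60. That is 18 − 2 + 1 = 17, plus (60 − 18)/2 = 21, so up to 38 scheduled on-treatment draws after Day 1, plus the follow-up visit. The stated item reduces these to the highest one.

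2. **What the maximum does for ANC.** Protocol Appendix 2 uses a fall below 1,000/µL and a recovery above 1,500/µL as its two marks. For a patient who passes both, the maximum exceeds 1,500/µL and the minimum is below 1,000/µL, however deep or long the fall. The maximum therefore carries no information about the event.

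3. **What else shows a fall in ANC.**
   - The worst-grade shift table. The worst CTCAE grade for a neutrophil count comes from the lowest value, so the patient in step 2 is counted there.
   - By-visit statistics. SAP 5.1 defines these as "mean, median, 25th percentile (Q1), 75th percentile (Q3), standard deviation, minimum and maximum", so the lowest ANC at each visit is printed.
   - Spaghetti plots, and listings that flag out-of-range values (SAP 11.2).
   - Neutropenia as an adverse event of interest, by patient and by severity (SAP 11.1).

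4. **What else shows a fall in WBC, lymphocytes or hemoglobin.** The by-visit statistics, plots and flagged listings apply. The shift tables do not, and none of the three is a named event of interest. Take a patient whose hemoglobin falls below 10 g/dL, the limit in exclusion criterion 3 (Protocol 6.2), and then recovers. That value can appear as the minimum across patients at one visit, but no planned laboratory table says how many patients ever fell that low.

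5. **Whether the sentence can be carried out.** There are three readings.
   - One maximum per patient over the whole period: it has no visit to be shown by.
   - A running maximum up to each visit: it can only stay level or rise.
   - The maximum across patients at each visit: SAP 5.1 already provides it.

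   None of the three gives a low extreme per patient.

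6. **Which measurements count.** SAP 11.3 says that the maximum and last blood pressure use scheduled and unscheduled visits. SAP 11.2 has no matching statement. Appendix 2 calls for ANC repeats within 72 hours and then at 72-hour intervals. These fall between monthly visits, so a patient's lowest ANC may be an unscheduled one. Leaving such values out could understate the worst grade in the ANC shift table.

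**The case against.** The strongest reply is that nothing about neutropenia depends on the maximum column. The same sentence also gives actual values and changes, and the graded worst-value shift for ANC, planned in the same section, shows neutropenia more directly than a mean minimum would. Step 3 bears this out, and it stands. A reader might infer that the SAP cannot show neutropenia, or that every test is summarized only by its maximum. The documents support neither.

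A second reply is that the protocol describes a drug-related fall only for ANC. That also stands. Protocol 3.6.3 reports dose-dependent decreases in ANC; Protocol 3.6 links cytopenias in lymphoma patients to prior treatment and underlying disease, and says that ITP patients had not manifested neutropenia. A reader should not infer that fostamatinib is known to lower WBC, lymphocytes or hemoglobin. The case for covering them is narrower: exclusion criterion 3 sets lower limits for all three, and SAP 4.5 names hematology. Because SAP 4.5 gives hematology only as an example, ANC alone could be said to satisfy it. The gap is therefore one of coverage and not a flat contradiction.

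A third reply is that a per-patient minimum has its own bias. The lowest of many noisy readings lies below the patient's usual level even with no drug effect, and an open-label study without a concurrent control cannot separate the two. This is correct, and it limits how the minimum should be read.

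**Conclusion.** The point holds in a limited form and is of low severity. The stated rule takes the wrong extreme for blood counts and, read as one value per patient, cannot be tabulated by visit. For ANC the consequence is one uninformative column, since other planned outputs show neutropenia. For WBC, lymphocytes and hemoglobin there is a real but modest gap: no worst-grade shift and no per-patient lowest value.

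No hypothesis test, confidence interval or efficacy result is affected. No numeric size is given, because the within-patient variability of these counts is not in the documents. The verdict assumes that the worst value in the shift tables means the worst by CTCAE grade, and that the maximum item covers hematology, as the section's opening suggests.

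**What to change.** Three changes to SAP 11.2:

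- Replace the maximum item with the worst post-baseline value, presented once per patient: the maximum for ALT, AST, ALP and bilirubin; the minimum for ANC, WBC, lymphocytes and hemoglobin. For any other test, either name a direction or leave the item out.
- Extend the worst-grade and last-grade CTCAE shift tables to WBC, lymphocytes and hemoglobin.
- State, as SAP 11.3 does for blood pressure, that unscheduled values count toward the worst and last values.

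The cost is a few lines of text, a minimum/maximum switch in the program and three more shift-table parameters: from 6 × 2 = 12 parameter-by-table summaries to 9 × 2 = 18. The hematology data are already collected. The one drawback is the chance lowering of a per-patient minimum, so a note should direct the reader to the graded shift tables alongside it.
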